8.3.1 Primary Efficacy Variable

The primary efficacy variable is the absolute change from baseline in ppFEV₁ (in percentage units) through Day 29 in each part.

ppFEV₁ is the ratio of FEV₁ (L) to the predicted FEV₁ (L), expressed as a percentage. The predicted FEV₁ will be calculated using the Quanjer GLI-2012 Regression Equations and Lookup Tables¹, adjusting for age, height, sex and ethnicity. Details are provided in [Appendix E](#).

8.3.1.1 Primary Analysis of the Primary Efficacy Variable

8.3.1.1.1 All Parts: Period 1 in the Treatment Period

The null hypothesis to be tested is that the mean absolute within-group change from baseline in ppFEV₁ through Day 29 is zero for VX-659 in TC with TEZ and either IVA or VX-561, for each part, separately. A 2-sided *p*-value of 0.05 or less will be interpreted as sufficient evidence to reject the null hypothesis.

The primary analysis will be performed using a mixed-effects model for repeated measures (MMRM) with change from baseline in ppFEV₁ as the dependent variable for each part, separately. For Part 1, the analysis will include 4 treatment groups: placebo, TC-low, TC-mid, and TC-high. For Part 2, the analysis will include 2 treatment groups: placebo + TEZ/IVA, and TC-high (VX-659 + TEZ/IVA). For Part 3, the analysis will include 2 treatment groups: placebo and TC2-high (VX-659+TEZ+VX-561). The model will include treatment group, visit, and treatment-by-visit interaction as fixed effects and subject as a random effect, with the continuous baseline ppFEV₁ as a covariate, and will include all data from each treatment group and visit during Period 1 in the analysis. The model will be estimated using restricted maximum likelihood. Denominator degrees of freedom for the F test for fixed effects will be estimated using the Kenward-Roger approximation. An unstructured covariance structure will be used to model the within-subject errors. If the model estimation does not converge, a reduced compound symmetry covariance structure will be used instead. Conditional on the observed data and covariates, missing ppFEV₁ data due to treatment or study discontinuation will be assumed to be missing at random; consequently, no imputation of missing data will be performed.

[figure not shown]
The adjusted means and 95% confidence intervals (CI) of the average treatment effect through Day 29 for each TC, with a 2-sided *p*-value will be estimated within MMRM using PROC MIXED in SAS, for all within-treatment and between-treatment comparisons, for each part, separately. Contrasts based on the fixed effects in the model, defined at the baseline covariate mean for the combined treatment groups using unique subjects in the FAS who have at least one post-baseline measurement through Day 29, will be used to estimate the average treatment effect across post-baseline visits through Day 29.

Further, the adjusted mean and 95% CI of the treatment difference between each TC group and placebo or TEZ/IVA at each post-baseline visit through Day 29 will be provided along with the corresponding *p*-value, for each part. In addition, the adjusted mean and 95% CI of the within-treatment difference at each post-baseline visit through Day 29 for each treatment group will be provided along with the *p*-value, for each part.

The adjusted mean (with 95% CI) obtained from the MMRM analysis at each post-baseline visit through Day 29 will be plotted by treatment group, for each part. In addition, a waterfall plot showing the subject-level absolute change in ppFEV₁ at Day 29 will be presented, by treatment group.

The primary analysis will use pre-dose measurements only. The post-dose measurements on the same day will be used for sensitivity analysis as described in the next section.

In addition, for each part, descriptive analyses of the change from baseline will be performed for all treatment groups by post-baseline visit through the safety follow-up visit.

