12.3.3 Efficacy Analysis

12.3.3.1 Analysis of Primary Efficacy Variables

The primary efficacy variable is the absolute change from baseline for ppFEV₁ through the Day 29 Visit in all parts. The analysis will be performed using a mixed-effects model for repeated measures (MMRM) with change from baseline as the dependent variable. The model will include treatment group, visit, and treatment-by-visit interaction as fixed effects, subject as random effect, and the continuous baseline ppFEV₁ as a covariate. The model will be estimated using restricted maximum likelihood. Denominator degrees of freedom for the F test for fixed effects will be estimated using the Kenward-Roger approximation. An unstructured covariance structure will be used to model the within-subject errors to account for repeated measures within a subject. If the model estimation does not converge, a compound symmetry covariance structure will be used. Conditional on observed data and covariates, missing data due to treatment or study discontinuation will be assumed to be missing at random.

Adjusted means and 95% confidence intervals of the average treatment effects through the Day 29 Visit, as applicable, with 2-sided *P* values, will be estimated within MMRM using Least Squares Means via PROC MIXED in SAS, for all within-group and between-group comparisons.

Sensitivity analyses for handling missing data due to treatment or study discontinuation will be described in the SAP.

Additional supportive analyses using Period 2 in Parts 1 and 2 will be described in the SAP. Subgroup analyses will also be described in the SAP.

There will be no multiplicity adjustment for performing multiple hypothesis tests.

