8.3.5 Pharmacodynamic Analysis

The sweat chloride measurement for a given visit will be calculated as the mean of the non-missing sweat chloride measurements obtained on the left and right arms at that visit. If one of the two arm measurements at a time point is missing, the other will be used as the mean. A volume ≥ 15 μL is required for an accurate determination of sweat chloride. Any results reported as having volume < 15 μL will be considered missing. Any sweat chloride values reported as < 10 mmol/L or > 160 mmol/L will be considered missing.

The analysis of the PD effect of VX-659 in combination with TEZ and either IVA or VX-561 in Parts 1, 2, and 3 on sweat chloride concentrations will be described in this section.

Descriptive analyses of the change from baseline will also be performed for all treatment groups by post-baseline visit.

8.3.5.1 Primary Analysis of the Dose Response trend of absolute change in sweat chloride from baseline through the Day 29 Visit (Part 1)

The null hypothesis to be tested is that the dose response of the mean absolute change from baseline through the Day 29 Visit for sweat chloride is not decreasing between placebo and the 3 dose levels of VX-659 with TEZ/IVA in Part 1. The test will be performed using the MCP procedure with the pre-specified contrasts provided in Section 6.2.2, within a linear MMRM framework using PROC GLIMMIX in SAS. The model will include treatment group, visit, and treatment-by-visit interaction as fixed effects and subject as a random effect, with continuous baseline ppFEV₁ and continuous baseline sweat chloride as covariates, and will include all data from all treatment groups and visits through the Day 29 Visit for analysis. The dose response test will be based on the 1-sided maximum *t*-statistic of the individual *t*-statistics for the multiple pre-specified contrasts at alpha = 5%, based on the treatment group means through the Day 29 Visit, using an unstructured covariance structure for the within-subject errors. If the model estimation does not converge, a reduced compound symmetry covariance structure will be used instead.

The tabular presentation of results for the average treatment effect across visits will be similar to the primary analysis of the primary efficacy variable for all parts. The corresponding *p*-value for the decreasing dose response trend will be provided.

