Sweat Chloride	Day 15 (predose)# Day 29 Day 33 Safety Follow-up	15 29 33 61	[1, 22] Use nominal visit, otherwise use (22, 31] Use nominal visit, otherwise use (31, 47] Use nominal visit
CFQ-R	Day 1 Day 15 Day 29	1 15 29	≤1 [1, 22] (22, 45]
Efficacy Assessment (Part 2)			
Spirometry	Day 1 (Baseline; before dosing)	1	≤1 Pre-dose
Sweat Chloride	Day 15 (predose)#	15	[1,22]
CFQ-R	Day 29 Day 43 Day 57 Safety Follow-up (Spirometry only)	29 43 57 85	(22, 36] (36, 50] (50, 71] Use nominal visit
Efficacy Assessment (Part 3)			
Spirometry	Day 1 (Baseline; before dosing)	1	≤1 Pre-dose
Sweat Chloride	Day 15 (predose)#	15	[1,22]
CFQ-R	Day 29 Safety Follow-up (no CFQ-R)	29 57	(22, 43] Use nominal visit
Notes:			
^a Visit name is used to report data in tables, listings and figures.			
^b Target day time point per protocol is predose, except for ECG and SP measurements.			

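### Does naming subject as a random effect beside an unstructured covariance make the primary MMRM unidentifiable?

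*SAP*

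**What the plan says.** For the primary analysis of change in ppFEV₁, SAP 8.3.1.1.1 specifies "treatment group, visit, and treatment-by-visit interaction as fixed effects and subject as a random effect", with baseline ppFEV₁ as a covariate, REML estimation and Kenward-Roger degrees of freedom. The same paragraph adds "An unstructured covariance structure will be used to model the within-subject errors" and then the fallback: "If the model estimation does not converge, a reduced compound symmetry covariance structure will be used instead". Protocol 12.3.3.1 makes the same pairing and gives the purpose of the matrix: "An unstructured covariance structure will be used to model the within-subject errors to account for repeated measures within a subject". The Part 1 sweat chloride trend model in SAP 8.3.5.1 also has a random subject term, "using an unstructured covariance structure for the within-subject errors". Relative change in ppFEV₁, CFQ-R respiratory score and sweat chloride (SAP 8.3.2.1, 8.3.2.2 and 8.3.5.2) follow the primary model.

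The primary model "will include all data from each treatment group and visit during Period 1 in the analysis", and "The primary analysis will use pre-dose measurements only". For Part 1 spirometry and sweat chloride, SAP Appendix B lists "Day 15 (predose)# Day 29 Day 33 Safety Follow-up" after baseline. Day 33 belongs to Period 2, so each subject contributes at most two post-baseline values, Day 15 and Day 29. The same two visits apply in Parts 2 and 3.

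Neither document says whether the random effect is a separate variance component or simply names the unit within which measurements are correlated.

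**The concern.** A covariance matrix for two visits has three distinct elements, and an unstructured matrix uses all three. A separate subject variance is a fourth parameter with no information left to estimate it. The fallback has the same feature, because compound symmetry already contains a common within-subject component.

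Coded literally, the fit has a flat direction and a singular information matrix for the covariance parameters. Kenward-Roger works from that matrix. If the software treated the singularity as non-convergence, the plan would move to compound symmetry because of its own text and not because of the data. Compound symmetry forces equal variances at Day 15 and Day 29, so Day 29 results could carry wrong standard errors. Those include the CFQ-R secondary endpoint and the by-visit ppFEV₁ contrasts.

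**Working it through.** **Inputs.** Model terms, fallback and data restriction: SAP 8.3.1.1.1. Visits: SAP Appendix B. Part 1 allocation 1:1:2:2 with about 54 subjects, hence 9, 9, 18 and 18: SAP Table 6-1. The documents give no figure for any covariance parameter. The only number attached to the primary endpoint is the power statement (18 per group, 7 points, at least 90%). It states no SD; a two-sided 5% one-sample t test reaches 90% if the SD is at most 8.63. It does not bear on this question.

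**1. Count the parameters.** Write the total covariance as V = σ_b²·J + R, where J is a matrix of ones and T is the number of visits. V has T(T+1)/2 distinct elements.

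| T | Unstructured + random subject: parameters / rank | Compound symmetry + random subject: parameters / rank |
|---|---|---|
| 2 | 4 / 3 | 3 / 2 |
| 3 | 7 / 6 | 3 / 2 |
| 4 | 11 / 10 | 3 / 2 |
| 8 | 37 / 36 | 3 / 2 |

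There is always exactly one redundant parameter. Having only two visits is not the cause. Without the separate random term, both structures are full rank at T = 2 (3 of 3 and 2 of 2).

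**2. What is undetermined.** Add a constant c to σ_b² and subtract c from every element of R: V does not change. The restricted likelihood, the estimates β̂ = (ΣX′V⁻¹X)⁻¹ΣX′V⁻¹y and their covariance (ΣX′V⁻¹X)⁻¹ depend on the covariance parameters only through V. The plan's contrasts are functions of β, so they are determined.

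**3. Numerical illustration.** One simulated Part 1 dataset: 54 subjects, two visits, four missing values, assumed means and covariance. REML was run with σ_b² held at 0, 5, 10 and 20. All four values gave the same row:

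| Structure | V: Day 15 variance, covariance, Day 29 variance | −2 restricted log-likelihood | TC-high average (SE) | TC-high minus placebo (SE) |
|---|---|---|---|---|
| Unstructured | 35.064, 34.465, 70.417 | 638.92166 | 11.3863 (1.576) | 11.4286 (2.757) |
| Compound symmetry | 52.543, 34.314, 52.543 | 649.34862 | 11.2731 (1.5725) | 11.145 (2.7591) |

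For example, at σ_b² = 20 the unstructured R is (15.064, 14.465, 50.417); adding 20 to each element returns V. The Hessian has one eigenvalue at zero in each case (about −6e-11 and 6e-19), which is the flat direction of step 2.

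**4. Does the literal model fail to fit?** In 100 simulated Part 1 datasets (about 6% missing at Day 29, assumed values), a general-purpose optimiser converged on the four-parameter model every time. The TC-high minus placebo difference matched the plain unstructured fit to within 0.0001 and its SE to within 0.001. A separate set of 60 datasets agreed, apart from one isolated optimiser discrepancy in an SE. With a generalised inverse of the information matrix, Kenward-Roger SEs and approximate degrees of freedom were the same with and without the extra term (difference about 1e-12). None of this was run in PROC MIXED.

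**5. If the fallback were triggered anyway.** The variance of the two-visit average is (v₁₁ + 2v₁₂ + v₂₂)/4. With complete data, compound symmetry replaces both variances by (v₁₁ + v₂₂)/2 and keeps v₁₂, giving ½[(v₁₁ + v₂₂)/2 + v₁₂], which is the same quantity. In the illustration, with four missing values: (35.064 + 2 × 34.465 + 70.417)/4 = 43.60 against (52.543 + 34.314)/2 = 43.43, a ratio of 0.998 on the SE scale. Across the 60 datasets the mean SE ratio was 0.995.

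For Day 29 alone, let r be Day 29 variance over Day 15 variance. The SE ratio is √[((1+r)/2)/r] and the actual size of a nominal 5% test is 2Φ(−1.96 × ratio):

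| r (assumed) | 0.5 | 0.67 | 0.8 | 1.25 | 1.5 | 2 |
|---|---|---|---|---|---|---|
| SE ratio | 1.225 | 1.118 | 1.061 | 0.949 | 0.913 | 0.866 |
| Type I error | 1.6% | 2.8% | 3.8% | 6.3% | 7.4% | 9.0% |

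The documents give no value for r, so the error could go either way.

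**6. Would another fallback help?** Heterogeneous compound symmetry at two visits has two variances and one correlation. Those 3 parameters make it the unstructured model again. The plan's compound symmetry, with 2, is the only genuinely simpler step.

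**The case for a change.** The best case for acting is that the fallback rule hinges on convergence, and the SAP does not say what to do with a fit that converges but has a singular Hessian. The primary model is assigned to PROC MIXED and the sweat chloride trend to PROC GLIMMIX, and the two might handle the redundancy differently. A few words would settle it.

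Part of this stands. The wording is redundant, the behaviour of those procedures has not been tested here, and the choice of structure is not wholly neutral. In the illustration, compound symmetry moved TC-high minus placebo from 11.43 to 11.15. That shift of 0.28 is about a tenth of its SE (0.28/2.757 = 0.10).

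The rest does not carry. The redundancy belongs to the specification and not to the data, so it appears on any dataset. Under SAP 9.1.1, code for the mid-study interim analyses is written by blinded staff on dummy treatment codes and dummy spirometry. A warning would therefore surface before any real result is seen. The ordinary response is to leave out the redundant term, and that alters no contrast. The results exposed to a wrong variance, by-visit estimates and CFQ-R at Day 29, support no multiplicity-controlled claim (SAP 8.1 and 8.3.2.3).

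**Conclusion.** This is loose wording, not a fault in the analysis. The protocol gives the unstructured matrix the job of handling repeated measures within a subject, so the natural reading is that the random effect names the grouping and no further variance is estimated. On that reading both structures are fully identified. On the literal reading one parameter is redundant, yet the total covariance, adjusted means, standard errors and treatment contrasts are unchanged.

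Editing the phrase would change no demonstrated result, and replacing the fallback with heterogeneous compound symmetry would remove the plan's only simpler model. If compound symmetry were reached for a spurious reason, the SE of the primary average would change by about half a percent (mean ratio 0.995), with larger effects in either direction confined to Day 29 results.

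This rests on simulated Part 1 data with assumed means and covariance, on modest missingness, and on general-purpose fitting instead of the named SAS procedures. The algebra in steps 1 and 2 needs none of those assumptions.

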^j Complete and abbreviated physical examinations (PEs) are described in Section 11.7.3. Symptom-directed PEs can be done at any time at the discretion of the investigator or healthcare provider.

^k Vital signs and pulse oximetry will be collected after the subject has been seated for at least 5 minutes.

^l Standard 12-lead ECGs will be performed after the subject has been rested for at least 5 minutes. On the Day 1 and 15 Visits, ECGs will be collected before dosing and 5 hours (± 1 hour) after dosing. At other visits, ECGs will be collected before dosing (as applicable). ECGs collected on the Day 1 Visit before dosing will be performed in triplicate.

^m See inclusion criterion 5 for information about the sweat chloride assessment for study eligibility. Sweat chloride assessments should be done at approximately the same time at every study visit during the Treatment Period and follow-up.

ⁿ At the Screening Visit, spirometry may be done pre- or post-bronchodilator. At other study visits, spirometry will be done pre-bronchodilator, before the in-clinic dose of study drugs, and should be performed at approximately the same time at every visit. On the Day 1 and 15 Visits, spirometry will also be performed 5 hours (± 1 hour) after the in-clinic dose of study drugs.

^o CFQ-R must be completed before the start of any other assessments scheduled at that visit.

^p The predose assessment on the Day 1 Visit may be performed on the previous day (Day -1) if randomization has occurred.

^q FSH will be measured for any potential postmenopausal female subjects with at least 12 months of continuous spontaneous amenorrhea.

Table 3-1 Study VX16-659-101 Part 1 (Subjects with F/MF genotypes): Schedule of Assessments

Event/Assessment ^a	Screening Period		Treatment Period (5 weeks)				ETT Visit ^b	Safety Follow-up 28 (± 7) Days After Last Dose
			Period 1 ^c (4 weeks)			Period 2		
	Screening Visit Days -28 to -1	Stratification Visit ^d Day -27 to -1	Day 1	Day 15 (± 2 days)	Day 29 (± 2 days)	Day 33 Visit ^e		
G6PD activity test ^f	X							
Serum chemistry and hematology ^g	X		X	X	X	X	X	
Coagulation ^g	X		X	X	X		X	
PK sampling ^h			X	X	X	X	X	
AEs, medications ⁱ , treatments, and procedures	Continuous from signing of the ICF through the Safety Follow-up Visit							

^f Blood samples will be collected for the G6PD activity test.

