9.1.3 Randomization

For all parts, randomization will be stratified by ppFEV₁ values (<70 vs ≥70).

For subjects in Part 1 and Part 3, the spirometry assessment used for stratification must be performed at least 14 days after the last dose of any previous CFTR modulator treatment. Therefore, subjects being treated with 1 or more CFTR modulators (investigational or approved) within 14 days of the Screening Visit must have a separate Stratification Visit at least 14 days after the subject's last CFTR modulator dose. For subjects not being treated with any CFTR modulators within 14 days of the Screening Visit, the Screening Visit spirometry assessment can be used for stratification.

For subjects in Part 2, the ppFEV₁ assessment for stratification of randomization will be done at the Day -14 Visit. See [Section 9.3.1](#).

Randomization will occur before the first dose of VX-659/control and may be done on either Day -1 or the Day 1 Visit, after all inclusion and exclusion criteria have been satisfied and the criteria for entry into the Treatment Period have been confirmed (see [Section 9.1.4](#)).

For Part 2, subjects who prematurely discontinue TEZ/IVA during the Run-in Period will not be randomized or participate in the Treatment Period, unless they rescreen and complete a 4-week Run-in Period ([Section 9.1.2](#)).

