9.3 Rationale for Study Design and Study Drug Regimens

9.3.1 Study Design

Stratification of Randomization

The extent of response to CFTR modulator treatment may depend on the subject's ppFEV₁ value (an index of disease severity) before the start of study drug dosing. Therefore, randomization in all parts will be stratified by pretreatment ppFEV₁ values, defined as the last ppFEV₁ measurement before treatment with VX-659. For Parts 1 and 3, this value is determined at screening, except for those subjects who require a Stratification Visit, in which case the value is determined at that visit. For Part 2, the pretreatment ppFEV₁ value is determined at the Day -14 Visit during the Run-In Period.

Control Treatments

Part 1 and Part 3: Efficacy has not been demonstrated for a corrector, potentiator, or any corrector/potentiator combination in subjects with F/MF genotypes. A Phase 3 study of TEZ/IVA in subjects with F/MF genotypes (Study VX14-661-107) was terminated following a planned interim futility analysis, which showed that the combination of TEZ/IVA did not result in a prespecified improvement in ppFEV₁. Because there is no effective treatment for this population, a placebo arm will be included as the control in Part 1 and Part 3.

Part 2: A Phase 3 study of TEZ/IVA (Study VX14-661-106) demonstrated a clinically meaningful benefit in subjects with the F/F genotype¹⁶; therefore, TEZ/IVA is the active control.

Run-in Period

Part 2 will have a 4-week run-in period to establish a reliable on-treatment (TEZ/IVA) baseline for comparison to Period 1, when subjects will additionally receive VX-659 or placebo.

Period 2

Part 1 and Part 2 include a second dosing period (Period 2), during which subjects will be administered TEZ/IVA. In Part 1, Period 2 is 4 days and is included to enable a more thorough evaluation of VX-659 exposure-response relationships by conducting PK and PD assessments during the VX-659 washout. In Part 2, Period 2 is 4 weeks to enable an assessment of PD and efficacy endpoints after VX-659 is washed out.

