6.3 Randomization

For all parts, randomization will be stratified by ppFEV₁ values (<70 vs ≥70).

For subjects in Part 1 and Part 3, the spirometry assessment used for stratification must be performed at least 14 days after the last dose of any previous CFTR modulator treatment. Therefore, subjects being treated with 1 or more CFTR modulators (investigational or approved) within 14 days of the Screening Visit must have a separate Stratification Visit at least 14 days after the subject's last CFTR modulator dose. For subjects not being treated with any CFTR modulators within 14 days of the Screening Visit, the Screening Visit spirometry assessment can be used for stratification.

For subjects in Part 2, the ppFEV₁ assessment for stratification of randomization will be done at the Day -14 Visit. See Section 9.3.1 of the protocol.

Randomization will occur before the first dose of VX-659/control and may be done on either Day -1 or the Day 1 Visit, after all inclusion and exclusion criteria have been satisfied and the criteria for entry into the Treatment Period have been confirmed (see Section 9.1.4 of the protocol).

For Part 2, subjects who prematurely discontinue TEZ/IVA during the Run-in Period will not be randomized or participate in the Treatment Period, unless they rescreen and complete a 4-week Run-in Period (Section 9.1.2 of the protocol).

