8 STATISTICAL ANALYSIS

8.1 General Considerations

The analysis will be performed for each part, and presented by treatment group and overall, for the Treatment Period, unless specified otherwise. The treatment groups are defined as follows:

- Part 1: *F508del*/MF genotype group
 - Placebo, TC-low, TC-mid, and TC-high.
- Part 2: *F508del*/*F508del* genotype group
 - TEZ/IVA and TC-high.
- Part 3: *F508del*/MF genotype group
 - Placebo and TC2-high.

The Schedule of Assessments is provided in [Appendix A](#). The precision standards for reporting safety and efficacy variables are provided in an internal Biometrics document that specifies the programming rules including the precision for derived variables.

All individual subject data for those randomized or dosed with any amount of study drug will be presented in data listings.

Continuous variables will be summarized using the following descriptive summary statistics: the number of subjects (n), mean, SD, standard error (SE), median, minimum value (min), and maximum value (max). SE may not be reported for safety summary tables.

Categorical variables will be summarized using counts and percentages. Percentages will be presented to 1 decimal place.

Baseline value, unless otherwise specified, will be defined as the most recent non-missing measurement (scheduled or unscheduled) collected before the first dose of study drug on Day 1 of the Treatment Period. For ECG, baseline will be defined as the most recent non-missing measurement (or the average of triplicate measurements, if the most recent non-missing measurement is obtained in triplicate), before the first dose of study drug on Day 1 of the Treatment Period.

Absolute change from baseline will be calculated as postbaseline value – baseline value.

Relative change from baseline will be calculated as (postbaseline value – baseline value)/baseline value.

Treatment-emergent (TE) period for Parts 1 and 3 will be from the first dose date of study drug in the Treatment Period until 28 days after the last dose date of study drug or end of study date (based on end of study visit in CRFs), whichever occurs first.

For Part 2, the TE period will be defined separately for the Run-In Period, and the Treatment Period:

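### The primary ppFEV₁ model leaves out the ppFEV₁ value used to stratify randomisation, an earlier pre-treatment measurement that is expected to improve precision at the cost of one degree of freedom

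*SAP*

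**What the plan says.** **Model.** Protocol 12.3.3.1 fits treatment group, visit and treatment-by-visit, with "subject as random effect, and the continuous baseline ppFEV₁ as a covariate". SAP 8.3.1.1.1 has the same terms, "with the continuous baseline ppFEV₁ as a covariate", and evaluates its contrasts at the mean of that covariate over the combined treatment groups. Neither section includes the stratum or the measurement behind it.

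**Stratification value.** Protocol 9.1.3 and SAP 6.3 stratify all parts at ppFEV₁ 70.
- Parts 1 and 3: for subjects without recent CFTR modulator use, "the Screening Visit spirometry assessment can be used for stratification". The others have a separate Stratification Visit.
- Part 2: "the ppFEV₁ assessment for stratification of randomization will be done at the Day -14 Visit".

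**Model baseline.** SAP 8.1 takes the "most recent non-missing measurement (scheduled or unscheduled) collected before the first dose of study drug on Day 1 of the Treatment Period". Spirometry is scheduled before dosing on Day 1 in all three parts, so this is normally the Day 1 value.

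**Other uses of the stratum.** In the SAP text available it appears only in a baseline summary (8.2.2) and a check for stratification errors (Appendix D).

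**The concern.** Protocol 9.3.1 stratifies because response may depend on pre-treatment ppFEV₁, so the sponsor regards the variable as informative. It is natural to think that a continuous baseline makes the stratum redundant. That would be so if both came from the same measurement, but they come from different visits.

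The outcome is change from the Day 1 value, so visit-to-visit error in that value enters every subject's change. An earlier value of the same quantity helps the model separate that error from the subject's usual level. Arms have about 6 to 18 subjects, so precision limits what each part can show.

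**Working it through.** **1. What the plan's power statement implies about the SD.** Protocol 12.1.1.2 and SAP 6.2.1.2 claim at least 90% power for a 7-point within-group change with n = 18, and state no SD. The claim cannot be reproduced, only inverted. At two-sided 0.05 a one-sample t-test needs an SD of at most 8.63. The normal approximation gives 7 × √18 / (1.960 + 1.282) = 9.16.

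**2. Best case, closed form.** Take equal variances at all visits (scaled to 1), correlation ρ between any two visits, two post-baseline visits, and the same response in every subject. The residual variance of the average change is:
- given baseline only: v₁ = (1+ρ)/2 − ρ²
- given baseline and the stratification value: v₂ = (1+ρ)/2 − 2ρ²/(1+ρ)

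| ρ | v₁ | v₂ | half-width ratio √(v₂/v₁) |
|---|---|---|---|
| 0.85 | 0.2025 | 0.1439 | 0.84 |
| 0.90 | 0.1400 | 0.0974 | 0.83 |
| 0.95 | 0.0725 | 0.0494 | 0.83 |

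If individual responses vary with SD σᵣ, then σᵣ² is added to both variances and the ratio moves towards 1.

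**3. Simulation at the planned sizes.** ANCOVA on the mean of the Day 15 and Day 29 changes, as a complete-data stand-in for the MMRM average. Arms are 9:9:18:18 (Part 1), 9:18 (Part 2) and 6:18 (Part 3), with stratified blocks and 1,500 runs per setting. Assumptions not taken from the documents: mean ppFEV₁ 62, between-subject SD 13, and the three SDs in the table. The screening value is kept within the eligibility range of 40 to 90. The SD of the average change is √(1.5σᵥ² + σᵣ²), with σᵥ the visit-to-visit SD; for example √(1.5 × 25 + 36) = 8.57.

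Entries are mean 95% CI half-width relative to the planned model, as the range over the three parts.

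| σᵥ | σᵣ | SD at stratification visit | SD of average change | Continuous, within | Continuous, between | Stratum, within | Stratum, between |
|---|---|---|---|---|---|---|---|
| 3 | 0 | 3 | 3.67 | 0.83–0.84 | 0.84–0.85 | 0.98 | 0.98–0.99 |
| 5 | 0 | 5 | 6.12 | 0.85–0.86 | 0.86–0.87 | 0.95–0.96 | 0.95–0.97 |
| 3 | 6 | 3 | 7.04 | 0.95–0.96 | 0.96–0.97 | 1.00 | 1.00–1.01 |
| 4 | 6 | 6 | 7.75 | 0.97 | 0.97–0.98 | 0.99 | 0.99–1.00 |
| 5 | 6 | 5 | 8.57 | 0.92–0.93 | 0.93–0.94 | 0.98 | 0.98–0.99 |
| 3 | 8 | 5 | 8.80 | 0.99 | 0.99–1.01 | 1.00 | 1.00–1.01 |

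Repeat simulations reached 1.02 for the continuous value and about 1.015 for the stratum, so I take the unfavourable end as about 1 to 2% wider.

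**4. Single trials.** These are averages. Across settings, the continuous value widened the interval in under 1% to 67% of runs, and the stratum in 13% to 74%.

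**5. Cost of the degree of freedom alone.** Ratio of 97.5% t quantiles: 49 to 48 df, 1.0005 (Part 1); 24 to 23 df, 1.0023 (Part 2); 21 to 20 df, 1.0031 (Part 3).

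**The case against.** - **The stratifying variable is already in the model in continuous form.** This stands against the two-level stratum, which adds little once the Day 1 value is included. It does not stand against the continuous earlier value, which is a separate measurement.
- **The gain depends on unknown variances.** This stands. The 13 to 17% gains need nearly uniform responses. In the settings with an SD of average change from 7.0 to 8.6, the within-group gain is about 3 to 8%. With a response SD of 8 it nearly vanishes.
- **The calculation is idealised for Parts 1 and 3, which are 78 of 105 subjects.** This also stands. "At the Screening Visit, spirometry may be done pre- or post-bronchodilator", and protocol 11.6.1 extends that allowance to the whole Screening Period. Screening can precede Day 1 by 28 days, and protocol 9.1.1.3 lets the window be extended by 2 to 4 weeks. After prior modulators, the stratifying spirometry needs 14 days of washout, against at least 4 weeks before Day 1. The earlier value is then a poorer proxy for the Day 1 level. The objection does not reach Part 2: the Day -14 value is taken on TEZ/IVA and pre-bronchodilator, in a run-in meant to establish a reliable on-treatment baseline.
- **Small parts cannot afford covariates.** This is hard to sustain. SAP 8.3.2.2 uses three covariates for CFQ-R in each part, including the 24-subject Part 3.
- **A stratum-adjusted analysis may exist elsewhere.** SAP 8.3.1.1.1 points to a sensitivity section that is not in the available text, so this cannot be excluded. It would not change the primary model.

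**Conclusion.** The point holds as one of efficiency. The primary ppFEV₁ model omits a pre-randomisation measurement that is already collected, differs from the model's baseline, and is expected to narrow the intervals at negligible cost. Under the assumed variances the continuous value changes the half-width by between about 17% narrower and 1 to 2% wider; the stratum alone by between about 5% narrower and 1 to 2% wider. These ranges rest on visit-to-visit SD 3 to 5, individual-response SD 0 to 8 and complete data, none of which the documents state. The case is clearest in Part 2 and weaker in Parts 1 and 3.

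Three stronger readings are tempting, and the documents do not support them:
- *Every ppFEV₁ interval is wider than it need be.* The gain is an expectation; a given trial's interval may widen slightly.
- *Omitting a stratification factor invalidates the analysis.* Treatment estimates stay unbiased and type I error is not inflated; intervals tend to be slightly conservative.
- *The same covariate belongs in the CFQ-R and sweat-chloride models.* The mechanism is Day 1 ppFEV₁ error inside a ppFEV₁ change. That error is not part of those outcomes, whose models already include baseline ppFEV₁ and their own baseline.

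**What to change.** In SAP 8.3.1.1.1 and protocol 12.3.3.1, add the continuous ppFEV₁ from the visit used for stratification as a second covariate. Do the same in the relative-change ppFEV₁ model (SAP 8.3.2.1).

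State where adjusted means are evaluated: at the mean of both covariates over the combined groups, extending the rule the SAP already has for one. This matters because the primary hypothesis is within-group, so the adjusted mean itself is tested.

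If the sponsor prefers the two-level stratum, weight the adjusted means by the observed stratum proportions; equal weights would move the within-group estimate to a 50:50 mix. If neither is added, give the reason.

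The cost is a short SAP amendment, which SAP section 3 allows before database lock, and one degree of freedom (0.05%, 0.23% and 0.31% on the t quantile in Parts 1, 2 and 3). No new data are needed.
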